#### 4.2.4 The nomela® analysis software

The nomela® test incorporates specific software for image analysis based on signal processing. This is not a machine-learning/neural network/AI system.

The Build version of the proprietary nomela® software to be tested in this clinical study will be nomela® 2 incorporating the iPad number and the iOS version.

After the pilot phase, the software will not be modified during the Study. The software cannot be influenced by the operator.

For this Study the Result page and Report page generated by the nomela® test will not be available to the operator.

#### 4.2.5 The nomela® test result

The nomela® software recognises the perimeter of the lesion from the close-up cropped image. Using non-scalar metrics of the image within the recognised perimeter and a combination algorithm of 5 predefined parameters a score is obtained. Based on the score the nomela® test assigns the lesion either to "no evidence of melanoma" (group N) or to "melanoma not excluded" (group R). Both groups contain benign lesions but group N should contain no melanomata.

All information from the test is transferred automatically to the Study Log. Completion of the nomela® test is normally shown on the device by a Result page. For this Study the result will not be available to the operator and research team but will be passed to the medical statisticians.

#### 4.2.6 Transfer, storage and retrieval of test information

Secure approved 4G connection enables uploading of the test information to secure approved storage.

No patient information or test information is retained on the nomela® device after this secure transfer.

(see Statements on Data Handling and Information Governance, Appendix D)

#### 4.2.7 Usability Assessments

Usability Assessments of the nomela® device and test will be obtained from investigator operators to satisfy regulatory requirements for medical devices in development. Forms for this purpose will be provided.

(see Appendix B3)

### 4.3 Clinical data collection

#### 4.3.1 Clinical data collection

The Study nomela® C8 is designed to eliminate paper case record forms and paper participant log. The nomela® test is electronic and is designed to eliminate transcription errors: the Patient(Participant) information, as hospital number, is captured by scanning at the start of the nomela® test. A cumulative Study database is populated automatically in a secure system. This information (except for the Result) is available to the authorised specialists and clinical research team accessible by approved systems.

(see 4.2.3)

(see Statement on the handling of Data, Appendix D) The (only) further information required for the Study is the histopathology diagnosis. This information is obtained from the Dept of Histopathology/ EPR by category by authorised personnel from Clinical Research/ Dermatology/Pathology requiring manual entry to the Study database. (see 4.3.4)

#### 4.3.2 Participant Information Sheet and Consent Form

Copies of the Participant Information Sheet and the completed e-Consent Forms will be stored securely for all participants at the Investigator site for subsequent central storage and archive by the Cambridge University Hospitals NHS Foundation Trust.

#### 4.3.3 The Study Database

The Study database will be populated by the nomela® output with the authorised user name/identifier, test date, time, place, hash-encrypted-

hospital-number, participant-lesion number, test images, nomela® reference, test result.

For addition of the code for the histopathology diagnosis category:

For details of encryption and transmission/storage:

see separate AppendixD1(2019b) including flow diagram The List of lesions tested by nomela® in the study period will be accessed by agreed process for the Department of Dermatology and Clinical Research.

Identification of Cases which were tested by nomela® in the Study will be independent of Moletest (Scotland) Ltd.

#### 4.3.4 Identification of diagnoses and Categorisation of Cases Accurate identification and linkage of (a) patient, lesion, nomela® test reference of image and result with (b) patient-lesion histopathology

report is crucial. The nomela® test includes accurate location visual information to aid this process.

The histopathological diagnosis will be collected by Clinical Research/ Dermatology from the Department of Pathology, Cambridge University Hospitals NHS Foundation Trust of those lesions completing the nomela® test.

### Manual entry of lesion diagnosis

The Study Log holding the Participant-Lesion Number and hospital number will allow manual interpolation of the histopathological diagnosis by category. The following categories of diagnosis will be used:

1 not melanoma

2.1 melanoma-in-situ (including lentigo maligna and acral lentiginous melanoma-in-situ)

- 2.2 melanoma superficial spreading
- 2.3 nodular melanoma
- 2.4 lentigo maligna melanoma
- 2.5 acral lentiginous melanoma
- 2.6 melanoma indeterminate
- 2.7 melanoma not otherwise defined
- 3 uncertain diagnosis
- 9 no information available/no biopsy

### Time limit

A time limit of 12 weeks from the end of the recruitment period will be set for the acquisition of histopathology diagnoses.

4.3.5 Case Lists

List of Cases

The List of Cases generated from the Study database will show:

Participant-lesion number (maximum of 9 lesions per participant) Hospital number Diagnostic category (histopathology)

(see 4.3.4 and Appendix C1)

Abbreviated List of Cases

The Abbreviated List of Cases generated from the Study database will show:

Participant-lesion number

Diagnostic category (histopathology)

nomela® test result

forming the Study Database for statistical analysis for forwarding to the University of Aberdeen.

(see Appendix C2)

# Lesions confirmed as melanoma during the Study period but which were not submitted to the nomela® test do not form the Cases for the Study.

# 4.4 Information security, transfer, retention and governance

4.4.1 Security of the nomela® device and data transmission to the Study database

NHS approved security will have been obtained for use of the nomela® device and for transmission of nomela® test data to the Study database.

After upload no images or other patient information are retained on the nomela® device. The only information held long-term on the nomela® device is the unique identifier for that iPad, the nomela® test software and the authorised user list for that nomela® device.

(see separate Statement from Moletest (Scotland) Ltd. on Data Handling and Information Governance and flow diagram)

### 4.4.2 Retention of study information

4.4.2.1.At the time of upload to the Study database the following information will be transferred securely to Moletest servers located in the UK: the nomela® device identifier, the authorised user for that test, the date of the test, the hash-encrypted-hospital number, the participant-lesion number, the test images, nomela® reference, raw data (5 parameters) and test result.

4.4.2.2 After upload to the Study database of the histopathology diagnosis the hash-encrypted-hospital-number will be automatically deleted so that retained information is without patient identifiable information.

4.4.2.3 Where no histology diagnosis has been discovered and entered to the database at 12 weeks after the nomela® test the hash-hospital-number is expunged automatically from the Moletest database.

#### 4.4.3 Information Governance

Moletest (Scotland) Ltd. recognises the importance of the highest standards for information governance.

The pathway to, location of and security of, the servers are described in the Statement on Data Handling Moletest (Scotland) Ltd. and Information Governance Flow Diagram.

(see separate documentation: Appendix D)

# 5.0 STATISTICAL CONSIDERATIONS: SAMPLE SIZE AND STATISTICAL ANALYSIS

Study Cases require both prior nomela® test result and diagnosis confirmed by histology of "not-melanoma" or of "melanoma".

### 5.1 Sample size:

For this Study a total sample generating a minimum of 200 confirmed melanoma Cases will be evaluated. Of those lesions referred for histology by the Department of Dermatology it is estimated that from 1 in 6 up to 1 in 10 are found to be melanoma and thus approximately 1200 to 2000 lesions will be tested.

#### 5.2 Statistical analyses:

5.2.1 Cases for the Study are defined as those cases of pigmented cutaneous moles referred for biopsy/excision by the dermatologist/plastic surgeon which satisfy the inclusion and exclusion criteria and are suitable for nomela® testing.

(see 3.1 - 3.3)

The data-set required for performance analysis will be:

the total number of nomela® tests performed during the study the number of tests excluded

the number of tests assigned to "no evidence of melanoma" (group

N)

the number of tests assigned to "melanoma not excluded" (group R) the number of not-melanoma cases in group N the number of melanoma cases in group N the number of not-melanoma cases in group R the number of melanoma cases in group R

5.2.2 Outcome measures

Primary outcome measure: sensitivity (95 % CI) of the nomela® test for not-melanoma.

Secondary outcome measure: the proportion (95% CI) of lesions that the nomela® test finds as having `no evidence of melanoma'.

5.2.3 The distribution of the nomela® test results between group N and R (see 1.4.3 & 3.6.2) for the Cases will be calculated. Estimates of sensitivity, specificity, positive and negative predictive values, and likelihood ratios (with 95% confidence intervals) will be calculated.

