#### 1.4 Summary of the clinical study C8

1.4.1 The nomela® technology is to be tested in this Study in secondary care by accumulating and analysing *in vivo* images of those pigmented skin lesions which are considered sufficiently suspicious to be referred by specialist dermatologist/plastic surgeon for biopsy/excision and histopathology. After a pilot phase of an initial 100 tests, the Study will involve testing 1200 to 2000 lesions such that completed tests on 200 melanoma have been accumulated.

1.4.2 The performance of nomela® will be assessed on all lesions tested by comparing the nomela® result (either "no evidence of melanoma" or "melanoma not excluded") with the subsequent confirmed diagnosis of "not-melanoma" or "melanoma" by histopathology.

(see Sections 4.2)

1.4.3 The ability to assign the lesions subjected to a nomela® test and subsequently confirmed as melanoma, to group R "melanoma not excluded" and by contrast not to group N "no evidence of melanoma" is to be evaluated.

Sensitivity and specificity of the nomela® test result for risk of melanoma will be determined. A high level of sensitivity is the objective.

(see 5.0) (see 1.4.3 and Appendix A2)

1.4.4 During the Study a participant's inclusion will not influence clinical management. There will be no change to routine care except for the short time required for the nomela® test.

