### 2.0 OBJECTIVES

1. To measure the performance of the **nomela**® test as a risk calculator for melanoma in pigmented skin lesions of patients referred by specialists for biopsy/excision and histopathology.

2. To demonstrate that the nomela  $\ensuremath{\mathbb{R}}$  test provides at least 95  $\pm$  2 % sensitivity for not-melanoma.

3. To complete a Usability Assessment (as per requirements of the relevant regulation covering medical devices EN62366).

4. Subsidiary objective: to construct a Health Economics Technology Assessment, details of which are developed separately.

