#### 3.8 Discordance limits

To avoid futile continuation of the Study where the nomela® test is demonstrably not performing as expected the Study shall be discontinued if the following condition is satisfied: when the nomela® tests for 15 melanoma are discordant ie where the nomela® result has been given as "No evidence of melanoma".

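### Objective 2 and the primary outcome are worded as sensitivity for not-melanoma, which is specificity for melanoma and contradicts 1.4.3, 4.2.5, the 200-melanoma sample size and the discordance limit

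*Protocol*

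**What the plan says.** Two controlling statements use the same wording.

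- Protocol 5.2.2: "Primary outcome measure: sensitivity (95 % CI) of the nomela® test for not-melanoma".
- Protocol 2.0, objective 2: the test is to provide at least 95 ± "2 % sensitivity for not-melanoma".

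Other sections describe a different quantity.

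- Protocol 1.4.3 evaluates whether confirmed melanomas go to group R and not to group N, and adds: "Sensitivity and specificity of the nomela® test result for risk of melanoma will be determined. A high level of sensitivity is the objective".
- Protocol 4.2.5 expects benign lesions in both groups and no melanoma in group N.
- Protocol 5.1: "For this Study a total sample generating a minimum of 200 confirmed melanoma Cases will be evaluated".
- Protocol 3.8 discontinues the study "when the nomela® tests for 15 melanoma are discordant", that is, when 15 melanomas have been given the group N result.

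Protocol 5.2.1 requires all four cells of the table of result by diagnosis. Protocol 5.2.3 lists sensitivity, specificity, predictive values and likelihood ratios with 95% confidence intervals, but does not say which condition or result counts as positive.

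**The concern.** Sensitivity for a condition is the proportion of lesions with that condition that receive the matching result. For not-melanoma the matching result is group N, so the stated quantity is P(N | not melanoma). With melanoma as the target condition, that is specificity.

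The purpose in 1.4.3 is P(R | melanoma). The two quantities use different rows of the table and different denominators. The literal one contains no melanoma at all, so it cannot show whether a rule-out test misses melanomas. The wording stands in both the objective and the primary outcome, so it cannot be passed over as a single slip. A statistician who follows 5.2.2 to the letter would report specificity as the main result and compare it with the target in objective 2.

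**Working it through.** **Inputs.** At least 200 melanomas, melanoma in 1 in 6 to 1 in 10 lesions, and 1200 to 2000 lesions (5.1). Limit of 15 discordant melanomas (3.8). Target 95 ± 2 % (objective 2). Moletest004, discriminator D1: 437 of 715 lesions in group N (Appendix A2).

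**1. The plan's own figure.** Total lesions = 200 / prevalence: 200 × 6 = 1200 and 200 × 10 = 2000. Both reproduce.

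**2. Denominators.** P(R | melanoma) rests on 200 lesions. P(N | not melanoma) rests on 1200 − 200 = 1000 to 2000 − 200 = 1800 lesions. The half-width of a 95% interval at 95% is 1.96 × √(0.95 × 0.05 / n):

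| Quantity | n | Half-width |
|---|---|---|
| P(R given melanoma) | 200 | ±3.0 points |
| P(N given not melanoma) | 1000 | ±1.35 points |
| P(N given not melanoma) | 1800 | ±1.01 points |

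A count of 200 melanomas is the natural way to size the first quantity. It does not set the precision of the second.

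**3. Response to missed melanomas.** Take 1200 lesions, 1000 of them not melanoma, with 950 of those in group N. Stay below the number of misses at which 3.8 stops the study:

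| Melanomas in group N | Primary outcome as worded | Sensitivity for melanoma |
|---|---|---|
| 0 | 950/1000 = 95.0% | 200/200 = 100% |
| 10 | 950/1000 = 95.0% | 190/200 = 95.0% |
| 14 | 950/1000 = 95.0% | 186/200 = 93.0% |

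The worded measure is the same in every row.

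**4. The discordance limit.** The lower edge of 95 ± 2 is 93%, which is 14 misses in 200. The fifteenth miss gives 185/200 = 92.5%, one case below that edge. The limit in 3.8 therefore lines up with objective 2 if the objective means sensitivity for melanoma. It has no relation to P(N | not melanoma).

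**5. Indication from Moletest004.** The 437 lesions in group N under D1 were 346 benign + 59 dysplasia + 32 other malignancies = 437, none of them melanoma, and 437/715 = 61.1% as reported. If m of the 715 were melanoma, P(N | not melanoma) = 437/(715 − m). The Protocol does not give m, so a range is assumed; its upper end is 715/6 ≈ 119.

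- m = 20: 437/695 = 62.9%
- m = 71 (about 1 in 10): 437/644 = 67.9%
- m = 119 (about 1 in 6): 437/596 = 73.3%

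Reaching 93% would need m ≈ 715 − 437/0.93 ≈ 245, and reaching 95% would need m = 715 − 437/0.95 = 255. Over the assumed range, the literal quantity is far below 95 ± 2 %.

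**The case against.** The strongest reply is that the intention can be recovered and nothing is lost. Sections 1.4.3, 3.8, 4.2.5 and 5.1 show what is meant. The wording probably comes from the rule-out purpose: 1.3 describes a tool that helps to exclude melanoma, and Appendix A2 (ix) speaks of screening out lesions that are not melanoma. Section 5.2.1 requires the count of melanomas in group N, and 5.2.3 requires both sensitivity and specificity, so P(R | melanoma) and its interval are computed whichever class is called positive. All of this stands. It limits the point to which estimate is primary and which carries the target. It does not remove the point, because the Protocol states the primary quantity wrongly in two places and 5.2.3 does not name the positive class. A statistical analysis plan may exist, but this is a contradiction inside the Protocol and not a detail left for later.

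A reader might infer more than the document supports:

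- *That missed melanomas go unreported.* They do not; see 5.2.1 and 5.2.3.
- *That a device could place every lesion in group N, score 100% and miss all 200 melanomas in this study.* The score is a property of the measure, but 3.8 would stop the study at 15 misses.
- *That the primary outcome carries a 95% target.* The 95 % in 5.2.2 is a confidence level. The target stands only in objective 2.
- *That the sample size is miscalculated.* Its arithmetic is right, and 5.1 states no precision or power formula. The conflict is one of purpose.
- *That the whole of the rest of the plan concerns sensitivity for melanoma.* The secondary outcome is the share of lesions in group N.
- *That Moletest004 predicts failure of objective 2 in C8.* That study enrolled primary-care referrals and its ranges were derived from its own diagnoses. C8 tests lesions already selected for biopsy, with software defined after a later study.

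**Conclusion.** The point holds. As worded, objective 2 and the primary outcome name P(N | not melanoma), in conflict with 1.4.3, 4.2.5, the purpose of 5.1 and the limit in 3.8. The primary result would stay at the same value while sensitivity for melanoma ranged from 100% down to 93.0%, and its denominator would be 1000 to 1800 lesions instead of the 200 melanomas that size the study.

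Three assumptions apply. The lower edge of 95 ± 2 is read as 93%, although the Protocol does not explain the ± 2. The 92.5% figure takes exactly 200 melanomas; 15 misses reached earlier would mean a lower observed sensitivity. The Moletest004 figures of 63% to 73% rest on an assumed 20 to 119 melanomas and are only an indication.

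The correction should be made before analysis because it decides what the headline claim of the study means, even though the data and the supporting estimates are already provided for.

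**What to change.** Make three wording changes in a protocol amendment.

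1. In 5.2.2, define the primary outcome as: *sensitivity of the nomela test for melanoma, i.e. the proportion of histologically confirmed melanoma Cases assigned to group R (melanoma not excluded), with 95% CI*.
2. In objective 2, attach the 95 ± 2 % target to that same quantity.
3. In 5.2.3, state that melanoma is the positive condition and group R the positive result. The specificity already listed there is then P(N | not melanoma), and the predictive values and likelihood ratios are fixed too.

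The cost is a few sentences. No extra lesions, data items or analyses are needed, because the four cells in 5.2.1 already supply the numbers.

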#### 6.0 Adverse Events Reporting and Safety Review

**6.1** Adverse Events are considered highly unlikely in this study and therefore it is not intended to collect information on adverse events on a routine basis nor conduct a Safety Review.

**6.2** Safety issues are as associated with the use of any Apple iPad for taking photographs. There is no direct contact of the device with the study patient.

**6.3** Safety review is not considered to be required since clinical management is not affected by acquisition of a nomela® test result.

# 7.0 REGULATORY ASPECTS; CLINICAL RESEARCH ETHICS REVIEW; MONITORING; ARCHIVE

Moletest (Scotland) Ltd. aims to adhere to ISO 14155:2011 Clinical investigation of medical devices for human subjects - Good clinical practice.

#### 7.1 Protocol registration

Moletest (Scotland) Ltd has obtained a Protocol Registration System account (organisation name: Moletest; administrator username [name]) with NIHR Clinical Research Network(CRN) Central Portfolio Management System (CPMS) to register nomela® Clinical Study C8 in anticipation of adoption to the NIHR Portfolio.

see [contact]

If not adopted, the Study Protocol C8 will be registered on the ISRCTN database.

see https://www.isrctn.com/

The Principal Investigator is [name], Consultant Dermatologist, Cambridge University Hospitals NHS Foundation Trust and Co-Investigators are [name], Consultant Pathologist, Cambridge University Hospitals NHS Foundation Trust and [name], Head, Media Studio, Cambridge University Hospitals NHS Foundation Trust.

#### 7.2 Medicines and Healthcare Products Regulatory Agency (MHRA)

The Moletest™ software technology has CE marking, under the Medical Devices Regulations 2002: regulation 19, as a Class I Device and specified as a dermatological differential (calculator) diagnostic aid. Notification was issued by MHRA dated 14 May 2014 reference CA014191.

see CA014191 Moletest UK Ltd. Letter from MHRA dated 2014 MHRA 4407 Medical Device Registration for Moletest (Scotland)- current Notify MHRA about a clinical investigation for a medical device- current

#### 7.3 Clinical Research Ethics Committee review

The Clinical Study Protocol and related documents will be submitted through IRAS for review and approval by an independent NHS Clinical Research Ethics Committee.

Any change of study protocol if significant and deemed necessary by the Principal Investigator(s) or by the Sponsor will be reported to the Clinical Research Ethics Committee in writing, and agreement obtained before implementation.

### 7.4 Study monitoring

Monitoring will be the responsibility of Moletest (Scotland) Ltd.

#### 7.5 Study data archive

All data will be held securely after completion of the Study according to ISO 14155:2011.

### 9.0 HEALTH ECONOMICS TECHNOLOGY ASSESSMENT

Health economic technology assessments have been commissioned to support the economic case for active deployment of nomela®.

#### APPENDIX A1&2 Moletest Ltd. reports to date

APPENDIX A1 Library-image based data

#### Summary of REPORT-007

Using library images of 43 benign, 44 dysplasia and 35 melanoma lesions, REPORT-007 shows that, as a result of improvements in identification to earlier algorithms regarding the perimeter of the lesion and effective filtering of unsuitable images, there were no outliers - i.e. the ranges for each condition were well defined and the App should not generate any missing values ([name] on file Moletest (UK) Ltd. Quality Management System).

APPENDIX A2 MOLETEST004 CLINICAL STUDY

#### SUMMARY

i) The performance of the Moletest™ technology (**nomela**®) was evaluated to assess its capability of discriminating pigmented skin lesions as benign from among those considered suspicious of skin malignancy including melanoma. The clinical study Moletest004 (NHS Lanarkshire L14100) (IRAS project ID: 159049) was approved by the NHS Research Ethics Committee, Cambridge South (15/EE/0097).

ii) A total of 1200 participants were recruited in hospitals in Lanarkshire, Scotland over a 12 month period starting in April 2015 in people referred from primary care for specialist dermatology review of suspicious pigmented moles. Recruitment followed presentation of a Participant Information Sheet and provision of written informed consent. The photographic images were taken by the Medical Illustration Service, using a dedicated iPad Air2 loaded with the **nomela**® technology. The study was managed by the Clinical Research Nurse team for NHS Lanarkshire for [name], Lead Skin Cancer Specialist.

iii) In the calibration phase the number of participants with eligible lesions was 381 and the number of eligible lesions was 447. One participant withdrew from this phase of the study. The calibration phase was used for refining the app user interface and improving technical aspects of image capture but not changing the underlying algorithms. The statistical analysis of the calibration phase was used to establish the usefulness of the methods employed.

iv) In the validation phase from 13 August 2015 to 25 April 2016 the number of participants recruited was 795. There were no patient

withdrawals. From 911 lesions some 715 were suitable for final analysis after 196 exclusions, some dual, for unmatched uploaded images (19), unsuitable images on inspection (95), unreturned biopsy results (6), unavailable final diagnosis (48) and incomplete valid measurements (35).

v) Considering the 715 lesions which have usable images, available diagnoses and all 5 proprietary signal processing measurements, 61.1% had at least one measurement beyond the range for 'melanoma' (D1). Of these 437 lesions, 346 were benign [79.2%], 59 dysplasia [13.5%] and 32 [7.3%] other malignancies.

To use the D1 discriminator would mean over 60% of lesions otherwise unassessed could exclude melanoma. In this discriminated group (N) about 80% are benign with about 13% dysplasia and 7% non-melanoma malignancy.

vi) When comparison is made beyond the range for 'melanoma or other malignancies' the discrimination (D2) may be more useful but is less powerful at 23.9% of lesions. Of these 171 lesions, 140 were benign [81.9%] and 31 dysplasia [18.1%].

To use the D2 discriminator would mean about 24% of lesions otherwise unassessed could exclude melanoma and all other skin malignancies. In this discriminated group (N) about 82% are benign with about 18% which are dysplasia irrespective of grade.

vii) A further revision of the range for each measurement for melanomaand-other-skin-malignancies to include approximately 90% of dysplastic lesions (D3), resulted in 18.0% of all lesions having at least one measurement beyond this range. Of these 129 lesions, 113 were benign [87.6%] and 16 were dysplastic [12.4%].

To use the D3 discriminator would mean about 18% of lesions otherwise unassessed could exclude melanoma and other skin malignancies and most dysplasias. In this discriminated group (N) about 88% are benign with 12% which are dysplasia irrespective of grade.

viii) Thus, in pigmented moles referred as suspicious of melanoma including other malignancy in this Study, after excluding 196 lesions for clinical, technical or data capture reasons, and using the 715 lesions with all 5 signal processing parameters available, **nomela®** was able to exclude melanoma, by using discriminator D1, in 61.1% of lesions.

Further **nomela**® was able to exclude melanoma and other skin malignancy, by using discriminator D2, in 23.9% of lesions or, alternatively to exclude melanoma and other skin malignancy and 90% of dysplasia, by using discriminator D3, in 18.0% of lesions.

Using D1 the low risk group (N) contains 79.2% which are benign, 13.5% which are dysplasia and 7.3% other non-melanoma malignancy. Using D2, the low risk group (N) contains 81.9% benign and 18.1% dysplasia. Using D3, the low risk group (N) contains 88% benign and 12% dysplasia.

ix) The principal aim of the technology is to provide a diagnostic aid to screen out, with sufficient confidence, lesions which are NOT melanoma. The cutaneous dysplasias are not life threatening and the majority require no treatment. Basal cell carcinoma is almost exclusively localised and slow-growing. Squamous cell carcinoma only rarely metastasises and is slow-growing. The results here suggest that it is possible, using the D1 discriminant, to exclude the potentially life-threatening melanoma in at least 60% of presenting lesions.

Increasing the discrimination performance leads to a smaller proportion of the total presenting for assessment which the technology separates into a low risk group. If it is deemed necessary to exclude all skin malignancies including melanoma it appears that the performance using D2 as discriminant function might also be considered useful and which is applicable to just under one-quarter of the total lesions presenting for assessment.

x) The clinical utility of **nomela**® on the basis of this evidence is that, with the cautions regarding relatively low absolute numbers of malignancies including melanoma in this study, it should be possible to deploy the technology in trained professional hands to assist in the diagnosis of pigmented moles. This may reduce the need for specialist review who are currently referred by 50-60%, with appropriate advice and caution. If this enables the services in primary and specialist care to focus efforts then this should lead to clinical and economic benefits. Further refinement of the **nomela**® technology will seek to shift the ratios to those which are even more useful.

